9.3.2.2 Secondary outcomes

Secondary outcomes

- Healthcare utilization outcomes: hospitalizations, emergency department (ED) visits, length of stay, number of filled drugs, outpatient visits
- All cause cost: Total cost of care, divided by medical (inpatient costs, outpatient costs, emergency costs) and pharmacy costs (all reported in Per Patient Per Month (PPPM) costs)

Exploratory outcomes

• Effectiveness outcomes: 2-point MACE as a Composite Score of myocardial infarction, stroke or coronary revascularization

9.3.2.3 Further outcomes

All pre-specified outcomes, which are not classified as primary or secondary, should be clearly identified as "further outcome" of interest and described as above.

9.4 DATA SOURCES

This study will utilize IQVIA's Real-World Data (RWD) Adjudicated Claims Database (formerly known as PharMetrics Plus). IQVIA's claims database is composed of more than 190 million unique enrollees from national and sub-national health plans and self-insured employer groups from 2006 to the present.¹⁵ The database is considered representative of the sex and age demographics of the insured United States population.¹⁶ The database contains a multitude of patient data points that are relevant for this study including:

- Demographic, geographic, and insurance type/enrollment information,
- Primary and specialty care visit dates and diagnosis codes,
- Medication use including refill dates, quantity, and days supplied, and
- Hospitalizations and emergency department visit dates, length of stay, and diagnosis codes

We anticipate having access to claims data that was generated though at least December 31, 2019. IQVIA's database has been extensively used in pharmacoepidemiological research. Recent examples include *Pandya et al.* (2020) and *Stolshek et al.* (2018).^{16,17} The claims data will be fully de-identified prior to receiving access for analyses.

9.5 STUDY SIZE

The following calculation is intended to estimate the number of events necessary to perform a powered analysis of the effect of add-on treatment with empagliflozin on the incidence of

hospitalization from heart failure. We will use the formula below for the power calculation for a two-group survival analysis:

$$N_e = \frac{(Z_\alpha + Z_\beta)^2}{[\log(HR)]^2 q_0 q_1}$$

where the significance level, α , will be set equal to 5% and the type 2 error threshold, β , will be set equal to 20%, resulting in a Z_{α} and Z_{β} of 0.96 and 0.842, respectively. The EMPA-REG OUTCOME clinical trial reported a hazard ratio of 0.65 (=*HR*), which we have applied in our sample size calculation. Given that there will be substantially more control subjects than treatment subjects and assuming the application of IPTW would have the effect of balancing the cohorts, we consider a range of possible proportions of the control and treatment arms of the study. Below we visualize scenarios with a minimum and maximum proportion of patients in the control arm equal to 0.5 and 0.9, respectively. This corresponds to a minimum and maximum number of events required for a powered analysis of 169 and 470.

Next we must consider the potential incidence rates of hospitalization from heart failure in our study population and the implied number of patients needed in our sample. We note, first, that the EMPA-REG OUTCOME clinical trial reported incidence rates of 14.5 and 9.4 events per 1,000 patient years for the placebo- and empagliflozin-administered arms, respectively. We note, second, that our study population will be at high-risk of cardiovascular events similar to the EMPA-REG OUTCOME study population. Furthermore, using previously referenced evidence of the higher risk of cardiovascular events in sulfonylurea-treated patients we assume that the incidence rate is, at best, equal to that of the placebo-administered population of the EMPA-REG OUTCOME study.

A reasonable scenario might assume that 80% of our patients are in the control arm and use the estimated weighted average of the control and treatment arms $(0.8 \times 14.5 + 0.2 \times 9.4 = 13.48)$ as the incidence rate and 265 events as the necessary number of events. This scenario would require 19,600 patient years available in the dataset.

Based on preliminary calculation stated below for IQVIA database, we believe there will be a sufficient sample size to conduct a powered analysis of the effect of empagliflozin use compared to either control arm. Nevertheless, the final decision of performing the analysis will

depend on the final sample size and the number of events accrued during the follow-up for primary outcome (*see key study outcomes section for details*)

Metformin Days Supply in PI	Empagliflozin Sample #	Metformin Sample size #		
No Metformin	582	75,563		
0 to 3 months	461	8,771		
3 to 6 months	331	10,409		
6 to 9 months	375	14,275		
9 to 12 months	801	17,029		
Total	2550	126,047		
* The final sample will be different, based on further data cleaning and further application of inclusion/exclusion criteria				

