	 E.g. Ischemic heart disease, hypertension, hyperlipidemia, chronic kidney disease, ischaemic or haemorrhagic stroke, peripheral arterial disease or surgery, oedema 		
	 Diabetes-related complications, 		
	 E.g. Diabetic neuropathy, diabetic retinopathy, hospitalized hypoglycemia 		
	 Use of diabetes drugs 		
	 Length of metformin use 		
	 Use of other medications 		
	 E.g. Angiotensin converting enzyme inhibitors, Beta-blockers, calcium-channel blockers 		
	 Lifestyle factors 		
	• E.g. Obesity, Overweight, smoker		
	 Previous healthcare utilization 		
	 E.g. Previous coronary revascularization, Endocrinologist visit within prior 30 days, Cardiologist visit within prior 30 days, etc. 		
	Outcomes:		
	Primary outcome		
	 First hospitalization for congestive heart failure (HHF) (we will first analyze this by looking at diagnosis code in any position, we will then run the analysis considering diagnosis coding in either the principal or secondary position). 		
	Secondary outcomes		
	 Healthcare utilization outcomes: hospitalizations, emergency department (ED) visits, length of stay, number of filled drugs, outpatient visits 		

	 All cause cost outcomes: Total cost of care, divided by medical (inpatient costs, outpatient costs, emergency costs) and pharmacy costs (all reported in Per Patient Per Month (PPPM) costs) Exploratory outcome Effectiveness outcomes: 2 point MACE as a Composite Score of myocardial infarction, stroke, or coronary revascularization 	
Data sources:	IQVIA's Real-World Data (RWD) Adjudicated Claims Database (formerly known as PharMetrics Plus)	
Study size:	See Study Size section below for detailed descripted of power calculations. Our estimation corresponds to a minimum and maximum number of events (HHF in both cohorts) required for a powered analysis of 169 and 470 total HHF events between both cohorts.	

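### The event targets for unequal arms (265 at 80% control, 470 at 90% control) give about 72% and 70% power at a hazard ratio of 0.65, not the stated 80%

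*Protocol*

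**What the plan says.** Section 9.5 computes the required number of heart-failure hospitalisations as Ne = (Zα + Zβ)² / {[log(HR)]² q0 q1}. The significance level "will be set equal to 5% and the type 2 error threshold" "will be set equal to 20%, resulting in a" pair of z-values printed as "of 0.96 and 0.842, respectively". On the effect size it says: "The EMPA-REG OUTCOME clinical trial reported a hazard ratio of 0.65". The quantities q0 and q1 are shares of patients, since the section considers a "minimum and maximum proportion of patients in the control arm equal to 0.5 and 0.9, respectively". It then states: "This corresponds to a minimum and maximum number of events required for a powered analysis of 169 and 470".

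For the scenario that it calls reasonable (80% control), it averages 14.5 and 9.4 events per 1,000 patient-years to 13.48 and takes "265 events as the necessary number of events. This scenario would require 19,600 patient years available in the dataset". The Study size entry of the abstract repeats the range as the number "required for a powered analysis of 169 and 470 total HHF events between both cohorts".

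**The concern.** The formula is accurate when each arm's share of events is close to its share of patients. That fails when the arms are unequal and the hazard ratio is well below 1. If the protective treatment sits in the small arm, that arm yields a smaller share of events than of patients, and the scarce events in the small arm determine the precision of the hazard ratio. The formula then overstates power.

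The targets are the only benchmark the protocol offers for calling the analysis powered. Section 9.5 makes the decision to perform the analysis depend on the final sample size and the events accrued. The Data analysis entry of the abstract makes the choice between propensity score matching and weighting depend on whether the matched sample is still powered. If 265 or 470 events were reached with unequal arms, a null result could be presented as coming from a study with 80% power when the chance of missing a hazard ratio of 0.65 was nearer 28–30%.

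**Working it through.** **Inputs (all from section 9.5).** Significance level 5%; type 2 error 20%; HR 0.65; control share of patients 0.5, 0.8 or 0.9; rates 14.5 (control) and 9.4 (empagliflozin) per 1,000 patient-years.

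**1. Reproduce the plan's figures.** With z = 1.96 and 0.842, (1.96 + 0.842)² = 7.851 and [log 0.65]² = 0.1856, so Ne = 42.3 / (q0 q1).

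- 50:50: 42.3 / 0.25 = 169
- 80:20: 42.3 / 0.16 = 264 (printed as 265)
- 90:10: 42.3 / 0.09 = 470

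The printed 0.96 would give only about 70, 109 and 194, so it is a misprint for 1.96 and plays no part in this point.

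**2. Event split at the planned effect.** With q1 the empagliflozin share of patients, its share of events is f = q1·HR / (q1·HR + q0).

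- 80:20: f = 0.13 / 0.93 = 14.0%, so 265 events split about 228 to 37.
- 90:10: f = 0.065 / 0.965 = 6.7%, so 470 events split about 438 to 32.

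The protocol's own weighted average shows the same: 0.2 × 9.4 = 1.88 of 13.48, or 13.9%.

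**3. Power at the printed targets.** Score-test approximation with the variance under the alternative: z = [√D (q1 − f) − 1.96 √(q0 q1)] / √(f(1 − f)).

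- 265 events, 80:20: (16.28 × 0.0602 − 0.784) / 0.3468 = 0.566, power 71.4%.
- 470 events, 90:10: (21.68 × 0.0326 − 0.588) / 0.2506 = 0.477, power 68.4%.
- 169 events, 50:50: (13 × 0.1061 − 0.98) / 0.4886 = 0.816, power 79.3%.

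Other methods, all two-sided at 5%:

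| Method | 265 (80:20) | 470 (90:10) |
|---|---|---|
| Wald approximation | 68.1% | 64.8% |
| Score approximation, alternative variance | 71.4% | 68.4% |
| Exact binomial on the event split | 73.4% | 70.6% |
| Exact, averaged over Poisson event counts | 71.6–74.0% | 68.6–72.2% |
| Survival simulation, protocol rates, 19,600 and 33,600 patient-years | 71–72% | 69–70% |
| Time-ordered simulation stopped at the exact event count | 72.5–73.6% | 70.1–70.2% |

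The survival simulations used exponential times and uniform censoring with a mean of 2 years, which is an assumption not found in the protocol. The time-ordered simulations did not need it. For 50:50 at 169 events, simulations ranged from about 77% to 81%.

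**4. Events needed for 80%.** D = [1.96 √(q0 q1) + 0.842 √(f(1 − f))]² / (q1 − f)².

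- 80:20: (0.784 + 0.292)² / 0.0602² ≈ 319 events; 319 / 0.01348 ≈ 23,700 patient-years, against 19,600.
- 90:10: (0.588 + 0.211)² / 0.0326² ≈ 599 events. The average rate is 0.9 × 14.5 + 0.1 × 9.4 = 13.99, so 599 / 0.01399 ≈ 42,800 patient-years, against 470 / 0.01399 ≈ 33,600.
- 50:50: about 172 events.

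Simulated at these targets, power was 78–81% (80:20) and 79–80% (90:10). The printed targets are therefore low by 1 − 265/319 = 17% and 1 − 470/599 = 22%.

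**The case against.** The formula is a standard planning approximation and was evaluated correctly, so there is no slip of arithmetic. Matching is the first choice, and in its simplest 1:1 form the relevant target is 169, which is nearly adequate. The unequal splits are offered as a range of scenarios, no numeric go/no-go threshold is set at 265 or 470, and the data already exist. The power figures above are for an unweighted analysis, whereas section 9.5 assumes that weighting balances the cohorts. Precise replacements such as 319 and 599 also hide a spread: across methods, the need runs from about 304 to 352 at 80:20 and from 564 to 674 at 90:10.

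Much of this is fair. The error is in what the approximation delivers, not in its evaluation. The shortfall is confined to unequal-arm analyses, and moving from 169 to 172 is trivial. The replacement counts depend on the method and are not validated for a weighted analysis.

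None of it restores 80%. No method reached that figure at 265 or 470 events. Unequal arms are the protocol's own working scenario and its stated maximum, and the section expects many more controls than treated patients. The preliminary table is more lopsided still: 2,550 on empagliflozin against 126,047 in the other column. Weighting can balance covariates but cannot add events among empagliflozin patients. A null result judged against these counts would still be credited with more power than the study had.

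**Conclusion.** The concern holds. At HR 0.65, 265 events with an 80:20 patient split give about 72% power (68–74% across methods), and 470 events with a 90:10 split give about 70% (65–72%). The stated 20% type 2 error is really about 28% and 30% in those scenarios. The equal-arm target of 169 is sound to within a point or two by calculation.

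This assumes proportional hazards, a two-sided 5% test, similar follow-up in the two arms, and an unweighted Cox or log-rank analysis. The loss of precision from weighting is not modelled and would not restore the power. The correction should be made, because the figures are relied on when judging whether the analysis is powered.

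**What to change.** In section 9.5, replace the unequal-arm targets using the formula in step 4 of the working: about 319 events and 23,700 patient-years at 80:20, and about 599 events and 42,800 patient-years at 90:10. Name the method used, since others move these counts. Change the upper figure in the abstract to match. The equal-arm 169 may stay, or be given as about 172 for consistency.

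Alternatively, keep 265 and 470 and state their power as about 72% and 70%. In either case, say that the counts are for an unweighted comparison.

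The cost is a short recalculation and the replacement of a few figures in two places. No data, follow-up or analysis method changes. The stated requirement becomes somewhat harder to meet.

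### The sufficient-sample statement in Protocol 9.5 is not supported by its own feasibility table, which counts ineligible patients and is never converted into expected events

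*Protocol*

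**What the plan says.** Protocol 9.5 uses a two-group survival formula with a hazard ratio of 0.65, alpha 5% and beta 20%, and prints the two Z values as "of 0.96 and 0.842, respectively". It considers a "minimum and maximum proportion of patients in the control arm equal to 0.5 and 0.9, respectively", giving 169 to 470 events. The abstract repeats this as the number "required for a powered analysis of 169 and 470 total HHF events between both cohorts". The balanced end of the range is motivated by "assuming the application of IPTW would have the effect of balancing the cohorts".

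The section then takes event rates of 14.5 (control) and 9.4 (empagliflozin) per 1,000 patient-years. It adds: "A reasonable scenario might assume that 80% of our patients are in the control arm". That scenario leads to 265 events and 19,600 patient-years.

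Finally it states that "we believe there will be a sufficient sample size to conduct a powered analysis of the effect of empagliflozin use", and shows a table of patients by pre-index metformin supply. A note says the final sample will differ, and the decision to analyse is left to the final sample size and event count.

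**The concern.** The sufficiency statement rests on a table whose largest comparator row, and second-largest empagliflozin row, consists of patients with no metformin. Section 9.2.2 requires prevalent metformin use in both arms. The control share in the table is also well outside the range used for the event calculation. In addition, the step from patient-years to patients is announced but not carried out: no mean follow-up and no expected event count appear.

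Two things are at stake. The primary outcome is described as the one the study is powered for (9.3.2.1), so an imprecise hazard ratio for heart-failure hospitalisation could be read as the result of an adequately sized comparison. And the abstract (Data analysis) makes the choice between propensity-score matching and IPTW depend on whether the matched sample is powered, so an unclear event target feeds into the choice of primary method.

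**Working it through.** **1. The protocol's figures.** Events = (Zα + Zβ)² / [(ln HR)² q0 q1], with ln 0.65 = −0.4308.
- With Zα = 1.96 and Zβ = 0.842: 7.851 / 0.1856 = 42.31, divided by q0 q1. This gives 169.2 at 50% control, 264.4 at 80% and 470.1 at 90%, matching 169, 265 and 470.
- With the printed 0.96 the results would be 70, 109 and 194. The printed value is a slip; the event counts already use 1.96.
- Patient-years at 80% control: 264.4 / 0.01348 ≈ 19,600, as stated.

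**2. Eligible counts (table in 9.5, criterion in 9.2.2).**
- Empagliflozin: 461 + 331 + 375 + 801 = 1,968 (= 2,550 − 582).
- Comparator: 8,771 + 10,409 + 14,275 + 17,029 = 50,484 (= 126,047 − 75,563). The column is headed Metformin; I assume sulfonylurea initiators.
- Control share: 50,484 / 52,452 = 96.2% (98.0% on the raw totals).

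**3. Events for the whole pool, as under the IPTW fallback.** 42.31 / (0.0375 × 0.9625) ≈ 1,172 events. Weighting adds no events to the small arm. Expected empagliflozin events are 1,968 × 9.4 / 1,000 = 18.5 per year of mean follow-up, whichever method is used.

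**4. Mean on-treatment follow-up needed for 80% power, and power at assumed follow-up.** Needed follow-up = required events / (average rate × patients). For 1:1, 169.2 / 0.01195 ≈ 14,160 patient-years, and 14,160 / 3,936 = 3.6 years. Power = Φ(√(events × q0 q1) × 0.4308 − 1.96).

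| Design | Events needed | Mean years needed | Events, power at 1 y | at 2 y | at 2.7 y |
|---|---|---|---|---|---|
| 1:1 | 169 | 3.60 | 47, 31% | 94, 55% | 127, 68% |
| 1:2 | 190 | 2.52 | 76, 42% | 151, 70% | 204, 83% |
| 1:3 | 226 | 2.17 | 104, 48% | 208, 77% | 281, 88% |
| 1:4 | 264 | 1.99 | 133, 51% | 265, 80% | 358, 90% |
| Full pool, no weighting loss | 1,172 | 1.56 | 750, 61% | 1,501, 89% | 2,026, 96% |

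The formula is generous when the arms are very unequal. Using the expected events per arm, power = Φ(0.4308 / √(1/d1 + 1/d0) − 1.96). For the full pool at 1 year (18.5 and 732 events) this is about 45%, and at 2.7 years about 85%.

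**5. Follow-up the calendar allows (9.1).** Index dates run from 1 January 2015 to 31 January 2020 and data end on 31 March 2020, so possible follow-up is 0.16 to 5.25 years. Under uniform entry the mean is (5.25 + 0.16) / 2 = 2.7 years if nobody is censored before the study end. Section 9.1 also stops follow-up at a gap of more than 30 days in either drug, a switch or addition, nursing home admission or disenrollment. Section 9.7.1 accepts up to 10% unmatched cases before changing the method; losing 10% raises the 1:1 requirement to 3.6 / 0.9 = 4.0 years.

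**6. Sensitivity to the rates.** For 1:1 to reach 169 events, both rates would have to be about 3.6 times the protocol's at 1 year, 1.8 times at 2 years or 1.33 times at 2.7 years.

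**The case against.** A reader might infer that the table proves the study cannot reach 80% power. The documents do not support that, for four reasons.
- 1:1 matching is not fixed. Section 9.7.1 allows two to four controls per case if more sample is needed, and both it and the abstract fall back to IPTW. Ratios of 1:1 to 1:4 correspond to 50% to 80% control, inside the planned range, so the 1,172 events concern only the whole-pool analysis.
- Mean follow-up and entry pattern are not given, and individual follow-up can reach 5.25 years. At 2.7 years, 1:2 to 1:4 matching exceeds 80% by formula.
- The control rate of 14.5 is treated as a floor, and the first analysis counts a heart-failure code in any position, so events may be more frequent.
- The statement is worded as a belief, and the analysis is made conditional on final size and events.

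All four stand against a claim of impossibility. They do not supply the missing support. The hedges leave ineligible patients in the counts behind the statement, no follow-up is assumed anywhere, and the alternatives reach 80% only at a follow-up that the protocol neither states nor justifies. The IPTW fallback is also where the 96.2% share applies, and balancing by weights does not lift the limit set by the empagliflozin events.

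**Conclusion.** The sufficiency statement is unsupported as written. Three parts need no outside assumption about follow-up: the no-metformin rows are ineligible; the eligible pool is 96.2% control (given the reading of the comparator column), so 470 is not the maximum for a whole-pool analysis; and patient-years are never turned into patients.

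On power, the conclusion depends on follow-up. At the protocol's rates and hazard ratio, 80% is implausible under 1:1, which needs 3.6 years against about 2.7 under uniform entry with no early censoring. For 1:2 to 1:4 or the full pool it is possible but not shown, needing about 1.6 to 2.5 years on treatment. Across 1 to 2.7 years, power runs from 31% to 68% for 1:1, 51% to 90% for 1:4, and 61% to 96% for the full pool before weighting loss. The range is wide because mean follow-up is not in the document.

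**What to change.** In 9.5 and in the abstract's study-size entry:
- drop the no-metformin row, and correct or confirm the label of the comparator column;
- state an assumed range for mean on-treatment follow-up and for the event rates;
- report expected events per arm, power and detectable hazard ratio for 1:1, 1:K and IPTW, using the effective sample size after weighting for IPTW (for example, 1:1 at 1 year: about 47 events, 31% power, detectable hazard ratio exp(−2.802 / √(47 × 0.25)) ≈ 0.44);
- extend the scenarios to the 96% control share, and remove the premise that IPTW balances the cohorts for power;
- restate or withdraw the sufficiency statement to match, so that the abstract's matching-or-IPTW rule refers to a defined event target;
- correct the printed Zα from 0.96 to 1.96, which changes no stated event count.

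Replacing the power statement with one about precision of the hazard ratio is optional. The cost is a short recalculation and wording in two places. The data are existing claims, so no recruitment is affected; the stated power will probably look less favourable.

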Evaluate clinical outcomes (specifically cardiovascular outcomes like hospitalization for heart failure), and healthcare cost, and resource utilization, among patients on empagliflozin as an add-on therapy to metformin versus patients on sulfonylureas as an add-on therapy to metformin, in patients with T2D and CVD.

Specifically our objectives are the following

- 1. Primary Objective
 - a. Compare incidence of HHF between the two aforementioned patient populations.
- 2. Secondary Economic Objectives
 - a. Comparisons of HCRU outcomes: hospitalizations, emergency department (ED) visits, length of stay, number of filled drugs, outpatient visits
 - b. Comparisons of all-cause cost outcomes: Total cost of care, divided by medical (inpatient costs, outpatient costs, emergency costs) and pharmacy costs (all reported in Per Patient Per Month (PPPM) costs)
- 3. Exploratory Objective
 - a. Comparisons of 2-Point MACE as a Composite Score of myocardial infarcton, stroke or coronary revascularization

9. **RESEARCH METHODS**

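### Section 9.5 makes running the primary HHF analysis depend, without a criterion, on the sample size and events observed, although the Abstract and section 9.7.1 commit to it unconditionally

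*Protocol*

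**What the plan says.** Section 8 of the protocol names one primary objective: "Compare incidence of HHF between the two aforementioned patient populations". Section 9.3.2.1 calls HHF the outcome for which the study is powered, and its results table has an HHF row with a hazard ratio and 95% CI. The Abstract (data analysis) and section 9.7.1, Step 3, both state that the hazard ratio for the primary outcome will be estimated by Cox regression. Neither attaches a condition.

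Section 9.5 gives the event requirement: "This corresponds to a minimum and maximum number of events required for a powered analysis of 169 and 470". It then expresses confidence ("we believe there will be a sufficient sample size to conduct a powered analysis of the effect of empagliflozin use"), but the next sentence says that whether the analysis is performed at all is to "depend on the final sample size and the number of events accrued during the follow-up for primary outcome". No minimum count and no decision-maker are named. The sentence refers to a key study outcomes section, and no section has that name. The nearest one, 9.3.2.1, describes an event-count feasibility check for the exploratory outcomes only.

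Elsewhere the protocol answers a small sample differently. The Abstract moves from matching to inverse probability of treatment weighting (IPTW) if the matched sample is underpowered. Section 9.7.1, Step 1, allows 2, 3 or 4 controls per case and ends its sequence of matching options in IPTW.

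**The concern.** The protocol commits to the primary analysis in two places and makes it optional in a third. The optional clause takes effect only after the sample and the primary events have been counted, and it has no numeric criterion.

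The data already exist, so fitting the Cox model exposes no patient and adds little cost. A go/no-go decision on power therefore protects little. What it adds is discretion over whether the only primary comparison is reported. Section 6 plans for the data to be in hand on 10/01/2020 and the analysis plan to be final on 06/07/2021, and the protocol does not say that those who count events will be unaware of treatment group. Whether an HHF result appears could then depend on what was seen, which is a route to selective reporting.

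**Working it through.** **1. The protocol's event requirement (section 9.5).** Inputs: HR 0.65, alpha 5%, beta 20%, control share 0.5 to 0.9. The formula is events = (Zα + Zβ)² / [(ln HR)² × q0 × q1]. With Zα = 1.96 and Zβ = 0.842, the numerator is 2.802² = 7.851, and (ln 0.65)² = 0.1856.

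- 50% control: 7.851 / (0.1856 × 0.25) = 169.2
- 80% control: 7.851 / (0.1856 × 0.16) = 264.4
- 90% control: 7.851 / (0.1856 × 0.09) = 470.1

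These reproduce the stated 169, 265 and 470. The printed z values, "of 0.96 and 0.842, respectively", do not: 0.96 would give 70, 109 and 194. The 0.96 is a misprint for 1.96 and does not affect this point. In the 80:20 scenario, 265 / 0.01348 = 19,659 patient years, against 19,600 stated.

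**2. Patients available (table in section 9.5).** Empagliflozin with any metformin supply: 2,550 − 582 = 1,968. Comparators with any metformin supply: 126,047 − 75,563 = 50,484. I take the column headed Metformin to be the sulfonylurea comparator pool.

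**3. Follow-up.** Mean on-treatment follow-up is not stated, so it is assumed over a range. The index window in section 9.1 (01/01/2015 to 1/31/2020, follow-up to 3/31/2020) allows between 0.16 and 5.25 years per patient. With uniform entry and no early censoring the mean is (0.16 + 5.25)/2 = 2.7 years. Censoring at a gap of more than 30 days in any study drug pulls it below that.

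**4. Expected events and power.** Rates are those of section 9.5: 14.5 (control) and 9.4 (empagliflozin) per 1,000 patient years. Events per year of mean follow-up are:

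- 1:1: 1,968 × (0.0145 + 0.0094) = 47.0
- 4:1: 1,968 × (4 × 0.0145 + 0.0094) = 132.6
- All comparators: 50,484 × 0.0145 + 1,968 × 0.0094 = 750.5

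Power = Φ(|ln HR| × √(events × q0 × q1) − 1.96).

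| Mean follow-up | 1:1 events (power) | 4:1 events (power) | All comparators, events (power) |
|---|---|---|---|
| 0.5 y | 24 (18%) | 66 (29%) | 375 (35%) |
| 1 y | 47 (31%) | 133 (51%) | 751 (61%) |
| 1.5 y | 71 (44%) | 199 (68%) | 1,126 (78%) |
| 2 y | 94 (55%) | 265 (80%) | 1,501 (89%) |
| 2.7 y | 127 (68%) | 358 (90%) | 2,026 (96%) |

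Mean follow-up needed for 80% power:

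- 1:1: 170 / 47.0 = 3.6 years
- 4:1: 265 / 132.6 = 2.0 years
- All comparators (96.2% control, 1,172 events needed): 1,172 / 750.5 = 1.56 years, before any variance inflation from weighting

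**5. Sensitivity to who is eligible.** If only the 9 to 12 month metformin row counts (801 empagliflozin patients), 1:1 matching needs 8.9 years, beyond the 5.25-year maximum. If all 2,550 counted, it needs 2.8 years and gives about 165 events at 2.7 years.

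**6. What a short count would still deliver.** At 47 events (18.5 and 28.5), SE = √(1/18.5 + 1/28.5) = 0.299, and exp(1.96 × 0.299) = 1.80. The 95% CI runs from HR ÷ 1.8 to HR × 1.8. That is wide but reportable.

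**The case against.** The strongest reply is that section 9.5 sets no cancellation rule. It presents 169 to 470 as events for a powered analysis and never says that a lower count stops the work. The stated response to a small matched sample is IPTW or more controls per case, and section 9.5 itself treats 80% control as a reasonable scenario. This stands, and it limits what can be said about consequences. It does not remove the conditional sentence.

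The figures are also open to challenge. Follow-up is assumed. Section 9.5 treats 14.5 as the lowest plausible sulfonylurea rate, so events could be higher. The patient counts are marked as preliminary. At the 5.25-year maximum even 1:1 matching would give 47.0 × 5.25 = 247 events, although a cohort mean at that maximum is unrealistic. All of this stands, so the event counts show only that the option might be used.

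The clause names totals and describes no look by arm, and the analysis it refers to might mean the whole study rather than HHF alone. So one cannot assert that cost results would be published without HHF. A numeric criterion might sit in the analysis plan, which is not shown and which section 6 dates before the analytic dataset (06/07/2021 against 07/02/2021). That would reduce the discretion, but the contradiction with the Abstract and section 9.7.1 would remain in the protocol.

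**Conclusion.** The point holds as a contradiction within the protocol and as an unspecified post-data option over the only primary analysis. It does not depend on any event count: the clause would be a weakness even if events proved ample.

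The option could realistically be used. With 1,968 empagliflozin patients and the protocol's rates, 1:1 matching falls short of 169 events at every mean follow-up up to 2.7 years. At 1 year or less, even the full comparator pool has no more than about 61% power. This rests on the assumed follow-up, on counting every row with any metformin supply, on reading the second column as the comparator pool, and on applying the quoted trial rates unchanged.

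A reader might infer that, on the protocol's own figures, the primary question will go unanswered. The documents do not support that. Mean follow-up is missing, no text ties cancellation to 169 events, and the documented alternatives reach 80% power at about 2 years (4:1) or about 1.6 years (full pool, before weighting inflation). The supported statement is that the question could go unanswered.

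**What to change.** Delete the conditional sentence in section 9.5. State in its place that the HHF analysis will be run and reported as a hazard ratio with 95% CI whatever the event count. Use the count only to choose between matching and IPTW, in line with the Abstract's existing provision for an underpowered matched sample, and to describe precision. If events fall short of the target, label the result imprecise. Remove the reference to the section that does not exist under that name.

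The edit is one or two sentences and needs no new data. The cost is that the sponsor commits in advance to reporting a primary result that may be imprecise.
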